### **CRITERIA FOR EVALUATING RESPONSE/STATISTICAL ANALYSIS**

The aims of this proposal are consistent with the initial sub-stages of Stage I developmental research described in the Stage Model of Behavioral Research (Rounsaville, Carroll & Onken, 2001). Primary Aim 1: To develop an adaptive text messaging program for problem drinking. 1A. Develop a brief assessment, normative feedback and list of text messages based on the PD intervention literature & obtain outside review from thought leaders. 1B. Survey 40 problem drinkers on overall SMS intervention preferences including message content and timing and frequency

preferences. 1C. Develop SMS intervention, review with thought leaders and pre-pilot and test with 10 problem drinkers and modify intervention based on feedback. Primary Aim 2: : To test whether the Tailored-adaptive treatment arm is superior to the content tailored only arm and the consequence messaging arm in reducing weekly drinking/drinks per drinking day and percent days heavy drinking over the course of the 12 week intervention. Hypothesis 2a: Tailored-adaptive (TA) arm will be superior to the content tailored only and consequence messaging study arms in weekly drinking/drinks per drinking day. Hypothesis 2b: Tailored-only messaging will be superior to consequence messaging in reducing weekly drinking/drinks per drinking day. Hypothesis 2c: All supportive messaging arms will be superior to assessment only in reducing weekly drinks weekly drinking/drinks per drinking day. Hypothesis 2a: TA will be superior to TO & CM in reducing weekly drinking/drinks per drinking day. Hypothesis 2b: TO will be superior to CM in reducing weekly drinks. Hypothesis 2c: All supportive messaging arms will be superior to EMA only in reducing weekly drinking/drinks per drinking day. Other outcomes include percent heavy drinking days and drinking days.

Data will be cleaned, summary variables created, missing data evaluated, and distributions assessed for normality. Equivalence of the random assignment of groups on key baseline characteristics will be assessed, and in the unlikely event that groups differ significantly on any characteristics, we will run analyses both with and without these variables as covariates to determine whether baseline differences may account for differences in outcomes. Gender and race/ethnicity differences will be evaluated and these variables included as covariates if they are correlated with outcomes. We will aggregate daily EMA into use weekly summary data, as it allows us to examine the trajectory of drinking patterns week by week over the course of the 12-week study.

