Similar to our current studies, the RAs will assess potential participants and when a question or concern is present, flag the case to have the clinician review the data and speak directly with the potential participant. RAs are trained to have a low threshold to speak with the clinician on duty and a clinician is available at all times during both

screening and follow-up appointments. We already had a double review of the first 20 clients where the RA and a trained therapist each independently spoke with the potential participant and there

**Randomization:** Once participants complete the baseline assessment they will receive the brief feedback on safe drinking levels and be automatically randomized into one of the five treatment arms stratified by gender, alcohol consumption, and readiness for change. The split for stratification is as follows: Gender: Male and Female; Severity: Above 24 drinks for men and above 21 drinks for women; Readiness score: 0-7 (low); 8-10 (high). Based on these scores separate envelopes are created (envelope randomization method), where the RA chooses an envelope and places the participant in one of the 5 study conditions randomly chosen. We stratify to ensure proper heterogeneity across groups. Each grouping has an equal number of study conditions to ensure any one group (e.g. male, high severity, high effort) is represented across groups. At the half-way point of the study, we will examine how well balanced each of the groups are with regard to the stratification variables and weight the conditions in the envelopes accordingly.

Individuals who drop out after randomization will not be replaced and we will conduct intent to treat analysis on all individuals who receive at least 1 day of text messages. While the research assistant will review the study arms with the participants in general during consent, individuals randomized to the different study arms will be given individualized instructions on what to expect. During the course of the intervention all participants will be allowed to call the RA for any reason and will be able to pause their messaging for 24 hour periods.

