Two sets of preliminary analyses will be performed. The first will determine whether there are important differences among the experimental cells despite randomization. Pretreatment drinks per week, heavy drinking days, effort to reduce drinking and demographic characteristics (age, gender) will be examined using two-way analyses of variance in order to measure comparability among the five groups (and the goal only group) and success of the randomization procedure. Data will also be examined for conformity to statistical assumptions of normality, and a square root transformation will be performed on skewed data. To further account for skewness, zero-inflation, or other departures from Normal response distributions, we will use response transformations or more complex models.

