This study is exploratory and meant to generate effect sizes. However, our primary exploratory hypothesis is that there will be an ordered effect across conditions such that TA results in a significantly greater reductions in drinking than TO, TO greater than CM, and CM greater than EMA only. The GO group will be analyzed separately and compared to each condition using logistical regression and entered into the full model with all conditions as a secondary analysis. Effect size estimates along with significance levels will be generated for all comparisons. A goal of the study is to determine a reasonable effect size estimate, to assist in planning larger studies of the intervention, if findings justify that next step. The critical effect size estimate is of drinking outcomes. The sample sizes of 30-40 per group (after 20% attrition) will provide reasonable estimates of the differences in means. We will carefully examine the issue of missing data using a random-effects approach to modeling different patterns of missed data across the data collection points of the study as specified by Hedeker and Gibbons (1997). As exploratory secondary analyses we will compare study arms on differences in key secondary outcome variables assessed at baseline and week 12 including week 12 alcohol related consequences and drinking norms among others using multiple linear regression with baseline values and control variables entered into the first step and dummy coded treatment arms entered into the second step. Because this is an intervention development study, we will also compare groups at week 12 on overall satisfaction with the intervention and perceived relevance of the intervention to their needs using ANCOVA.

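### Covariates for the primary drinking outcomes enter only through baseline significance tests or outcome correlation, while baseline drinking and the stratification factors are not fixed in the analysis

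*Protocol*

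**What the plan says.** All references are to the Protocol.

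- **Criteria for Evaluating Response/Statistical Analysis**, first rule: "in the unlikely event that groups differ significantly on any characteristics, we will run analyses both with and without these variables as covariates". Neither version is named as the main result.
- Same section, second rule, for gender and race/ethnicity: "these variables included as covariates if they are correlated with outcomes". No threshold, outcome or time point is given.
- **Experimental Design, Randomization**: allocation to five arms is "stratified by gender, alcohol consumption, and readiness for change", each split in two. At the half-way point the team will look at balance on these factors and "weight the conditions in the envelopes accordingly".
- **Data Management & Analysis**, preliminary analyses: "Pretreatment drinks per week, heavy drinking days, effort to reduce drinking and demographic characteristics (age, gender) will be examined" by arm, "using two-way analyses of variance in order to measure comparability among the five groups (and the goal only group"), also as a measure of how well randomisation worked.
- Same section, secondary outcomes: arms are compared "using multiple linear regression with baseline values and control variables entered into the first step". No such sentence exists for the two primary outcomes. The nearest model wording is "We will carefully examine the issue of missing data using a random-effects approach to modeling different patterns of missed data", which lists no covariates.
- **Measures & Schedule of Events**: the 90-day drinking questionnaire (QFV-90) is taken at baseline and week 12.

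**The concern.** After a proper randomisation, a significant baseline difference between arms is a chance event. It does not show whether a variable predicts the outcome, and prediction is what makes adjustment worthwhile. Here the rule is also misdirected: stratifying on consumption all but removes the imbalance that would trigger adjustment for baseline drinking.

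The second rule makes gender conditional although it is a stratification factor. Since no outcome is specified, the two primary outcomes could end up with different covariates. The sounder approach, baseline values always in the model, is reserved for the secondary outcomes.

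At stake is the quality of the effect sizes, which the protocol gives as the reason for the study. An analysis that ignores strata and baseline reports intervals wider than the design warrants, and paired results with no stated main version leave a choice to be made after the data are seen.

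**Working it through.** **Sample size first.** The protocol gives 240 participants and 30-40 per group after 20% attrition. 240/5 × 0.8 = 38.4 and 240/6 × 0.8 = 32. Both lie in the stated range. I use 38 per arm (190 analysed).

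**Assumptions not in the documents.** Two-sided alpha 0.05; baseline-outcome correlation ρ of 0.3, 0.5 or 0.7; outcome SD of 1; severity split at the median of a normal baseline; gender and readiness unrelated to outcome.

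**Reported interval.** The unadjusted half-width is 1.96 × √(2/38) = 0.45 SD. With baseline in the model it is multiplied by √(1 − ρ²).

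| ρ | √(1 − ρ²) | adjusted half-width (SD) |
|---|---|---|
| 0.3 | 0.954 | 0.43 |
| 0.5 | 0.866 | 0.39 |
| 0.7 | 0.714 | 0.32 |

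**True precision under stratified allocation.** Stratifying on consumption already balances part of baseline drinking. A median split explains 2/π = 0.637 of the variance of a normal variable. The unadjusted estimate therefore has true variance proportional to 1 − 0.637ρ², against 1 − ρ² when baseline is adjusted for. The unadjusted test still uses a variance of 1, so its actual type I error is 2 × [1 − Φ(1.96/√(1 − 0.637ρ²))].

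| ρ | 1 − 0.637ρ² | 1 − ρ² | fall in true SE | type I error, unadjusted |
|---|---|---|---|---|
| 0.3 | 0.943 | 0.91 | 1.7% | 4.4% |
| 0.5 | 0.841 | 0.75 | 5.6% | 3.3% |
| 0.7 | 0.688 | 0.51 | 13.9% | 1.8% |

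**Simulation check.** With five arms, 190 analysed, eight strata, blocks of 5 and 4,000 runs per setting, the SE fell from 0.226 to 0.223, from 0.210 to 0.197 and from 0.191 to 0.163 (1%, 6% and 15%). Type I error was 4.6%, 3.5% and 1.9% unadjusted, and 5.2%, 4.8% and 5.0% with baseline fixed. Closed form and simulation agree within simulation error. Rounded: SE falls of about 2%, 6% and 15%, and type I error of about 4%, 3.4% and 2%.

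**What the trigger does.** In the same simulation, arms differed significantly on baseline drinking in 0 to 0.03% of trials, against 5-6% without stratification. Adjusting only when triggered gave the same SE as never adjusting.

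**Side by side.** The Goal Only arm is described under Study Treatments as a group into which people concerned about confidentiality are placed, to be analysed separately. The preliminary analyses nevertheless include it in the comparison that is meant to show whether randomisation succeeded.

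**The case against.** **The covariate list belongs in the SAP, and silence is not a choice.** This stands in part. The protocol states no full primary model, and baseline is listed among the collection points for the primary outcomes, so it could enter as a repeated response or a change score. The unadjusted comparator is therefore conditional. But the two covariate rules are written in the protocol and are poor as written.

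**The with/without pair is only a sensitivity check.** Its stated purpose is to see whether baseline differences explain outcome differences, and both results would be reported. That is fair, but a sensitivity check needs a named main analysis.

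**The correlation may be low.** The Experimental Design overview measures the primary outcomes by weekly text-message assessment, whereas baseline uses QFV-90 over a longer recall window, in people selected above a consumption threshold. That makes 0.7 optimistic, and at 0.3 the gain is small.

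**Stronger readings the documents do not support.**
- A reader might multiply five tests at 5% into a 23% chance of a significant difference and call the protocol's expectation wrong. That assumes independent tests and no stratification. Gender, drinks per week and effort to reduce drinking are stratification factors or close to them. Under stratified allocation the chance for the five named variables is about 7% (5-9%, depending on how closely heavy drinking days track drinks per week). The protocol's expectation is reasonable for these variables.
- A reader might turn 1/(1 − ρ²) into 33% to 96% more participants at ρ of 0.5 and 0.7. That ignores the precision stratification has already delivered.
- A reader might infer inflated false positives. The unadjusted test is conservative; inflation would need someone to pick the better of the two reported results.
- A reader might infer that Goal Only could trigger adjustment in the main analysis. The trigger sentence concerns randomly assigned groups, and Goal Only is analysed separately. Only the wording of the preliminary analysis is at fault.

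**Conclusion.** The concern holds as a poorly chosen rule stated in the protocol, and it is worth changing. The rule would almost never bring in baseline drinking and leaves the stratification factors to chance. If nothing else adjusts the primary comparison, reported half-widths are about 0.45 SD where 0.43, 0.39 or 0.32 is attainable. The gain in true precision is smaller: about 2%, 6% or 15% in standard error. These sizes rest on 38 per arm, the assumed correlations, and a near-median severity split; the documents give no correlation. The harm is overly wide intervals, conservative tests and no single main estimate.

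The planned mid-trial re-weighting of envelopes adds a reason to keep the strata in the model: if weights come to differ by stratum, allocation depends on stratum. The exploratory label does not remove the point, because the protocol wants effect sizes and significance levels for planning a larger trial.

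**What to change.** In Criteria for Evaluating Response/Statistical Analysis:

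1. Name one primary model for each drinking outcome that always includes arm, baseline drinking (the QFV-90 counterpart of that outcome, continuous), gender, severity stratum and readiness stratum.
2. Remove baseline significance and correlation with outcome as reasons to add covariates.
3. Label any further adjustment, including race/ethnicity, as sensitivity analysis.

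In the preliminary analyses under Data Management & Analysis, limit the check of randomisation to the five randomised arms and describe Goal Only separately.

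The cost is a change of wording. The stratification factors and baseline drinking are already collected before allocation, so no new data, visits or participants are needed. The model spends a few degrees of freedom out of about 190 analysed.

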#### Data Management & Analysis

Analyses will be conducted separately on two overlapping samples. All randomized subjects who received at least two days of text messages will be included in the first set of analyses as long as they have some follow-up data on primary analyses. This represents our main outcome analysis. We also will conduct a “worst-case” analysis in which subjects lost to attrition will use their pre-treatment drinking as their week 12 drinking data. Finally, in step three, we will conduct “completer analyses” on those patients completing a full course of messaging. This latter approach to analysis, although subject to more bias, attempts to provide an estimate of the maximal effect of the treatments under ideal conditions. Similar results with all three approaches would increase confidence in the findings. Effect size estimates along with significance levels will be generated for all comparisons. A goal of the study is to determine a reasonable effect size estimate and to assist in planning larger studies of the intervention if findings justify that next step. The critical effect size estimate is of drinking outcomes. The sample sizes of 30-40 per group will provide reasonable estimates of the differences in means.

There are two primary outcome variables: 1) Average drinks per week (sum of drinks drinking day) over the course of the study and 2) the percent of total days in which there is heavy drinking over the course of the study; This data will be collected via the Baseline, Week 4 and Week 12 assessments. Various summary statistics will also be computed, and significantly skewed distributions will be appropriately transformed prior to statistical analysis (e.g. Shapiro–Wilk test). As exploratory secondary analyses we will compare study arms on differences in key secondary outcome variables assessed at baseline and week 12 including alcohol related consequences and drinking norms.

Two sets of preliminary analyses will be performed. The first will determine whether there are important differences among the experimental cells despite randomization. Pretreatment drinks per week, heavy drinking days, effort to reduce drinking and demographic characteristics (age, gender) will be examined using two-way analyses of variance in order to measure comparability among the five groups (and the goal only group) and success of the randomization procedure. Data will also be examined for conformity to statistical assumptions of normality, and a square root transformation will be performed on skewed data. To further account for skewness, zero-inflation, or other departures from Normal response distributions, we will use response transformations or more complex models.

This study is exploratory and meant to generate effect sizes. However, our primary exploratory hypothesis is that there will be an ordered effect across conditions such that TA results in a significantly greater reductions in drinking than TO, TO greater than CM, and CM greater than EMA only. The GO group will be analyzed separately and compared to each condition using logistical regression and entered into the full model with all conditions as a secondary analysis. Effect size estimates along with significance levels will be generated for all comparisons. A goal of the study is to determine a reasonable effect size estimate, to assist in planning larger studies of the intervention, if findings justify that next step. The critical effect size estimate is of drinking outcomes. The sample sizes of 30-40 per group (after 20% attrition) will provide reasonable estimates of the differences in means. We will carefully examine the issue of missing data using a random-effects approach to modeling different patterns of missed data across the data collection points of the study as specified by Hedeker and Gibbons (1997). As exploratory secondary analyses we will compare study arms on differences in key secondary outcome variables assessed at baseline and week 12 including week 12 alcohol related consequences and drinking norms among others using multiple linear regression with baseline values and control variables entered into the first step and dummy coded treatment arms entered into the second step. Because this is an intervention development study, we will also compare groups at week 12 on overall satisfaction with the intervention and perceived relevance of the intervention to their needs using ANCOVA.

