**Ecological Momentary Assessment Only (EMA):** The EMA only arm will include the four weekly EMA items (Commitment to change (1x week), drinking days, average drinks per drinking day, number of heavy drinking days). Because intensive EMA can be an intervention within itself due to ongoing self-monitoring EMA across all conditions will be limited to three days and five total messages including three messages about weekly drinking sent on Sunday early afternoon. The EMA condition is designed to test whether brief feedback and weekly monitoring can reduce PD compared to active SMS interventions. The EMA only condition will send individuals assessment messages only (e.g. how committed are you to not drink heavily in the next 24 hours or how many days this week did you drink alcohol).

**No Alcohol Messages (Goal Only):** Messages that are general goal directed messages without the mention of alcohol will be offered to all individuals who are concerned about confidentiality. At present - we have placed 15 people in this group. While we will assess this group compared to other groups, they will be analyzed separately because of forced randomization. The "Goal Only" group was created to protect the safety of participants who were concerned about confidentiality and includes messages that are very general and do not explicitly refer to drinking or alcohol e.g. "Remembering your goals tonight when you go out will help you realize them tomorrow".

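### The protocol defines its main analysis set twice, incompatibly, and the set it calls the main outcome analysis is not intent-to-treat

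*Protocol*

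**What the plan says.** The protocol fixes the analysis population in two places.

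- **Experimental Design, Randomization.** Dropouts after randomisation are not replaced, and "we will conduct intent to treat analysis on all individuals who receive at least 1 day of text messages". No follow-up data are required.
- **Data Management & Analysis.** "All randomized subjects who received at least two days of text messages will be included in the first set of analyses". The sentence then restricts this set to people with outcome data after baseline. Of the resulting set the protocol says: "This represents our main outcome analysis".

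Two supporting analyses follow in the same section. One is a worst-case analysis in which "subjects lost to attrition will use their pre-treatment drinking as their week 12 drinking data". The other is a completer analysis of people who finished the full course of messaging. The statistical section later adds a random-effects approach to patterns of missing data.

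Message schedules differ by arm. Under Study Treatments, the tailored-only (TO), consequence and benefit arms get one message every evening. In the control arm, "The EMA only condition will send individuals assessment messages only", and "EMA across all conditions will be limited to three days and five total messages". The tailored-adaptive (TA) arm has adaptive timing and frequency, with no fixed daily schedule.

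**The concern.** An analyst cannot follow both definitions, and nothing in the protocol says which governs. The choice could therefore be made after the data are seen.

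The definition labelled as main also selects on two events that occur after randomisation: receiving a second day of messages and returning follow-up data. If either is related to the arm or to drinking, the groups compared are no longer the groups randomised. The contrasts with EMA only, which are central to the Primary Aim and Hypothesis 2c, then lose part of that protection. The study exists to supply effect sizes for a larger trial, so any selection in the main set would carry over into that trial's planning.

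**Working it through.** **1. The two definitions side by side**

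| | Randomization paragraph | Data Management & Analysis |
|---|---|---|
| Message days required | 1 | 2 |
| Follow-up data required | no | yes |
| Label | intent to treat | main outcome analysis |

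Someone with one message day, or with many message days but no follow-up, belongs to the first set and not to the second.

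**2. The plan's own sample figure**

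Inputs: 240 people, five randomised arms, 20% attrition, 30–40 analysed per group.

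- 240 / 5 = 48; 48 × 0.8 = 38.4.
- If the 15 goal-only people count within the 240: 225 / 5 = 45; 45 × 0.8 = 36.
- If six equal groups: 240 / 6 = 40; 40 × 0.8 = 32.
- If 20% take the goal-only option: 192 / 5 = 38.4; 38.4 × 0.8 = 30.7.

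All lie within 30–40, so the figure reproduces and is not in dispute. With everyone randomised analysed, the arms would hold 48 (or 45) each.

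**3. The follow-up condition**

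0.20 × 240 = 48 people at most (0.20 × 225 = 45 without the goal-only group), if everyone counted as attrition has no follow-up data. The true number depends on what counts as follow-up, and the protocol gives two answers. Experimental Design measures the primary outcomes by weekly EMA. Data Management & Analysis takes them from the baseline, week 4 and week 12 assessments. On the second reading, someone who returns EMA for three weeks and then leaves has no primary follow-up and is excluded.

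This loss need not be random. Under Adverse Events, a significant increase in drinking since baseline leads to withdrawal from the study. Someone withdrawn for that reason before week 4, with no later assessment, would fall out of the main set on the second reading.

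**4. The two-day rule**

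Assume that three EMA days means three per week, that Sunday is one of them, and that start days are spread evenly over the week. Count the start day as day 1. Let the gaps between message days be g1, g2 and g3, with g1 + g2 + g3 = 7. Summed over the seven start days, the day on which the second message day falls is

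[(g1 + g2 + g3)² + 7] / 2 = (49 + 7) / 2 = 28, so the mean is 28 / 7 = day 4.0 for every layout.

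Check with Sunday/Tuesday/Thursday: 3, 4, 3, 5, 4, 5, 4 for starts from Sunday to Saturday; sum 28, mean 4.0. Over all layouts the range is day 2 to day 6. The TO, consequence and benefit arms qualify on day 2. If EMA occupied only two days a week, the mean would be day 4.9 to 5.7; with Sunday only, day 11.

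The share excluded before day t under a constant daily dropout hazard h is 1 − exp[−h(t − 1)]. The dropout patterns are assumptions:

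| Assumed dropout | h | Daily arms, t = 2 | EMA only, t = 4 | Difference |
|---|---|---|---|---|
| 20% over 84 days | −ln(0.8)/84 = 0.00266 | 0.3% | 0.8% | 0.5 points |
| 10% in week 1 | −ln(0.9)/7 = 0.01505 | 1.5% | 4.4% | 2.9 points |

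In an arm of 48, the extra exclusion is about 0.25 person (48 × 0.0053) to 1.4 people (48 × 0.029).

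**The case against.** The strongest reply is that the arm-specific part of the concern is thin, and much of that stands.

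- A reader might infer that EMA-only participants meet both conditions later. The protocol does not support this. Weekly EMA and the week 4 and week 12 assessments run on the same schedule in every arm, so only the message-day condition can be met later.
- A reader might infer that someone leaving on day 3 is kept in a daily arm and lost from EMA only. That person would usually have no week 4 or week 12 data and would fail the follow-up condition in either arm. The two-day rule acts separately only in uncommon cases, such as stopping texts within days but still completing a web survey.
- The timing gap is not shown for TA, and the EMA days are given no stated period. The reminders to all arms described under Discomforts and Risks have no stated frequency and could bring the EMA-only arm's second message day forward.
- The protocol already plans a worst-case analysis and random-effects modelling of missing data, looks for agreement across its approaches, and calls itself exploratory.

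The last point softens the consequence without removing the fault. The worst-case analysis is supporting, and it is not said to restore people with fewer than two message days. The completer analysis is narrower still. A random-effects model cannot recover people whom the set definition has already left out.

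**Conclusion.** The contradiction and the post-randomisation selection are certain from the text. This is an error in a rule the protocol states, not detail left to an analysis plan.

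The follow-up condition is the larger problem: up to about 48 of 240, if the stated 20% attrition means no follow-up data. Whether that loss differs by arm is unknown. The two-day rule adds about 0.5 to 3 percentage points of exclusion in EMA only compared with the three daily arms, given three EMA days per week and the dropout patterns assumed above. Fewer EMA days would widen this gap, and reminders would narrow it.

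A reader might go further and put a figure on the bias. Multiplying an assumed 5–10 point difference in exclusion by an assumed gap of 5–10 drinks per week gives 0.25–1.0 drinks per week. The documents supply neither input, and the timing calculation does not yield a 5–10 point difference. No bias size can be derived.

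Severity: should be fixed.

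**What to change.** Replace both sentences with one definition: the main analysis includes every participant randomised to the five arms, in the assigned arm, regardless of messages received. The goal-only group, which is not randomised, stays separate as already planned.

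Analyse the repeated drinking data with the random-effects (likelihood) approach the protocol already names, with baseline included as one of the repeated measurements so that people without follow-up are retained. People with baseline data alone add little to the arm contrast. Keeping them makes the set the randomised one and leaves the missing-data assumption open to view. The same edit should say which assessments supply the primary outcomes.

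Keep the two-day, with-follow-up set and the worst-case analysis as labelled sensitivity analyses.

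Cost: protocol or SAP wording and minor programming; no extra data.
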